Secondary	
[A] Correlate histopathology findings with tracer uptake in the lymph nodes.
 
[B] Radiologically evaluate the drainage pattern of Sienna+ tracer using a high resolution MRI, to establish a baseline for individual variation.
 
EX-VIVO part of study:
 
[C] Measure the distribution and spread of the Sienna+ tracer using the SentiMag hand-held probe in mesorectal specimen after rectal cancer surgery (in the pathology department). This is to establish a baseline in individual variation between specimens.
 
[D] Assess the accuracy of the SentiMag hand-held probe/Sienna+ tracer in identifying "sentinel" lymph nodes. This will be determined in conjunction with a pathologist who will systematically identify lymph nodes in the standard manner. The level of tracer activity in each lymph node will be measured and correlated with position and tumour cell involvement.
 
IN-VIVO part of study:
 
[E] Establish feasibility of sentinel lymph node biopsy during localised surgery for early rectal cancer using SentiMag hand-held probe to identify "peaks" of tracer activity intro-operatively.
	
[A] Correlation between histopathology findings and tracer uptake (determined by Sentimag probe) in the lymph nodes.
 
[B] High-resolution MRI mapping of the drainage pattern of Sienna+ tracer.
 
EX-VIVO part of the study:
 
[C] Mapping of the distribution of Sienna+ tracer in the mesorectal specimen using the SentiMag hand-held probe after rectal cancer surgery.
 
[D] Accuracy of the SentiMag hand-held probe/Sienna+ tracer in identifying "sentinel" lymph nodes, determined by correlation with histopathology findings.
 
IN-VIVO part of study:
 
[E] Number of TEM operations where the "sentinel" lymph node could be identified during surgery using the Sentimag probe, and then successfully removed.

Device name	Magtrace® tracer and SentiMag® magnetometer	
Device Manufacturer	Endomagnetics, Cambridge	
Device Classification	Class IIa device	

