## 5. OBJECTIVES AND OUTCOME MEASURES/ENDPOINTS

Objectives	Outcome Measures/Endpoints

Primary Objectives
 
Establish feasibility of identifying sentinel lymph node in rectal cancer:
 
[A] Adverse or hypersensitivity reactions after tracer injection in rectal cancer patients.
 
[B] Establish whether tracer is still present and detectable at the tumour injection site and in the lymph nodes at the time of surgery.
 
[C] Determine the impact of tracer injection on subsequent surgery (e.g. any difficulties due to discolouration or inflammation of tissue planes
	
[A] Frequency of adverse or hypersensitivity reaction.
 
[B] Frequency of tracer being detectable at the tumour injection site and in the lymph nodes at the time of surgery.
 
[C] Surgeon’s assessment of any difficulties encountered attributable to prior tracer injection

Secondary Objectives
 
[A] Correlate histopathology findings with tracer uptake in the lymph nodes.
 
[B] Radiologically evaluate the drainage pattern of tracer using a high resolution MRI, to establish a baseline for individual variation.
 
EX-VIVO part of study:
 
[C] Measure the distribution and spread of the tracer using the SentiMag hand-held probe in mesorectal specimen after rectal cancer surgery (in the pathology department). This is to establish a baseline in individual variation between specimens.
 
[D] Assess the accuracy of the SentiMag hand-held probe/ tracer in identifying "sentinel" lymph nodes. This will be determined in conjunction
	
[A] Correlation between histopathology findings and tracer uptake (determined by Sentimag probe) in the lymph nodes.
 
[B] High-resolution MRI mapping of the drainage pattern of tracer.
 
EX-VIVO part of the study:
 
[C] Mapping of the distribution of tracer in the mesorectal specimen using the SentiMag hand-held probe after rectal cancer surgery.
 
[D] Accuracy of the SentiMag hand-held probe/ tracer in identifying "sentinel" lymph nodes, determined by correlation with histopathology

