
with a pathologist who will systematically identify lymph nodes in the standard manner. The level of tracer activity in each lymph node will be measured and correlated with position and tumour cell involvement.
 
IN-VIVO part of study:
 
[E] Establish feasibility of sentinel lymph node biopsy during localised surgery for early rectal cancer using SentiMag hand-held probe to identify "peaks" of tracer activity intra-operatively.
	
findings.
 
IN-VIVO part of study:
 
[E] Number of TEM operations where the "sentinel" lymph node could be identified during surgery using the Sentimag probe, and then successfully removed.

Tertiary Objectives Not applicable
	
Not applicable

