Intra-operative detection of the sentinel lymph node using the SentiMag probe and excision of the identified node (second part participants only): During rectal cancer surgery, following excision of the tumour, the surgeon will use the hand held SentiMag probe to identify the sentinel lymph node. This will then be dissected and removed for subsequent histological analysis.

Post-operative monitoring: Following surgery patients will be admitted to the colorectal ward for routine post-operative care. During this time they will be monitored and any adverse reactions or post-operative complications will be recorded. The patients’ participation in the study will cease when they are discharged from hospital.

Ex-vivo detection of the sentinel lymph node in the surgical specimen using the SentiMag probe (first part only): The SentiMag probe will be used to measure the distribution of the tracer and to identify the sentinel lymph node in the specimen removed during the standard surgical procedure. A Near InfraRed (NIR) imaging system will also be used to assess the specimen to detect the distribution of ICG as an adjunct to identifying lymph nodes.

Ex-vivo histological assessment of the surgical specimen: A colorectal pathologist will examine the tissue removed during surgery to identify all the lymph nodes present and whether or not they contain metastatic cancer deposits, according to standard practice. At the conclusion of the study the samples will be held in the cellular pathology department, in line with standard practice for diagnostic surgical specimens.

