## **12. STATISTICS**

### **12.1. Description of Statistical Methods**

All data will be stored in an Excel worksheet and analysed using Excel and R.

Frequency of event (adverse, hypersensitivity or complication) will equate to: number of adverse event/total number of recruited patients.

Frequency of tracer detection at surgery (at tumour site and in lymph nodes) will equate to: number of operations where tracer seen/ total number of operations on recruited patients.

Impact of tracer injection on subsequent surgery will be assessed by the surgeon's binary assessment as to whether surgery was more difficult than expected, and also free text comments to be analysed qualitatively.

A sentinel lymph node will be defined as the first lymph node draining the tumour and positivity defined according to the manufacturer's instructions. A "positive" node will be defined as having over 10% of the tracer activity of the site of initial submucosal injection. A "negative" node will be defined as having less than 10% of the tracer activity of the site of initial submucosal injection.

The detection rate for sentinel lymph nodes on MRI scan and Sentimag probe assessment will equate to: number of patients/specimens in whom a sentinel lymph node is identified/total number of examined patients/specimens.

MRI and Sentimag mapping will be qualitatively compared for all relevant patients/specimens (as appropriate) to establish a baseline of individual variability.

The presence and location of lymph nodes in the mesorectal specimen will be compared with the pathology findings for each patient in the ex-vivo part using correlation.

The success rate for removing the sentinel lymph node during TEM surgery will equate to: number of patients in whom the sentinel lymph node was removed/total number of patients undergoing TEM operation.

As this is a feasibility study, results will be continuously evaluated and adjustments made to the tracer dosage and timing of injection if indicated.

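### Section 12.1 correlates the presence and location of nodes with pathology, so it does not estimate the uptake-against-histopathology outcome A or the per-node part of objective D

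*Combined protocol and SAP*

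**What the plan says.** Sections 2 and 5 word secondary outcome A as "Correlation between histopathology findings and tracer uptake (determined by Sentimag probe) in the lymph nodes". It stands above the ex-vivo and in-vivo subheadings, so it is not confined to either part. Secondary objective D, in the ex-vivo part, adds: "The level of tracer activity in each lymph node will be measured and correlated with position and tumour cell involvement". The matching outcome measure D in the synopsis reads "Accuracy of the SentiMag hand-held probe/Sienna+ tracer in identifying 'sentinel' lymph nodes, determined by correlation with histopathology findings".

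Section 8 says that a colorectal pathologist will "identify all the lymph nodes present and whether or not they contain metastatic cancer deposits, according to standard practice".

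Section 12.1 contains one sentence that sets anything against pathology: "The presence and location of lymph nodes in the mesorectal specimen will be compared with the pathology findings for each patient in the ex-vivo part". It ends by naming correlation, without saying which coefficient or which unit. Elsewhere 12.1 gives an uptake rule ("A 'positive' node will be defined as having over 10% of the tracer activity of the site of initial submucosal injection") and a detection rate ("number of patients/specimens in whom a sentinel lymph node is identified/total number of examined patients/specimens"). Neither is compared with pathology.

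**The concern.** The variable that makes this a tracer study is how much tracer each node took up. It is in outcome A and objective D but not in the 12.1 sentence meant to analyse them, and neither is tumour involvement. An analyst who works from 12.1 would report a correlation that answers a different question.

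The substitute is also a poor guide to sentinel accuracy. The pathologist looks for every node, whereas 12.1 defines a sentinel node as the first one draining the tumour. Close agreement between a probe map and a complete node map could show only that tracer had spread everywhere.

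Section 12.2 recruits the 20 ex-vivo patients to establish the accuracy of sentinel node detection. This comparison is therefore a main product of that part, although the outcomes are secondary.

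**Working it through.** **Step 1: the plan's own figure.** The only figure bearing on this point is the sample size: 20 ex-vivo + 20 in-vivo = 40, as in the synopsis. Section 12.2 bases the ex-vivo 20 on earlier studies, and 12.3 disclaims a significance level, so there is no power calculation to reproduce. The point rests mainly on comparing texts.

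**Step 2: the texts side by side.**

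| Source | Probe-side variable | Pathology-side variable | Scope |
|---|---|---|---|
| Outcome A (2, 5) | tracer uptake in the nodes | histopathology findings | both parts |
| Objective D (2, 5) | activity level in each node | position and tumour involvement | ex-vivo |
| Outcome D (2, 5) | identification of sentinel nodes | histopathology findings | ex-vivo |
| 12.1 pathology sentence | presence and location of nodes | pathology findings, not itemised | ex-vivo, per patient |
| 12.1 10% rule | uptake above or below threshold | none | not stated |
| 12.1 detection rate | sentinel node identified, yes or no | none | patients or specimens |

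No row from 12.1 pairs uptake with pathology. Location does correspond to position in objective D; uptake and tumour status have no counterpart. In 12.1 a positive node is one with high tracer activity, not one with metastasis, so that wording does not bring tumour status in.

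**Step 3: which tracer would the 12.1 statistic favour?** Take the reading of probe-found nodes against all pathologist-found nodes. With n nodes per specimen and k sentinel nodes, a perfectly selective tracer matches a share k/n. For assumed k = 1 to 3 and n = 10 to 20, this runs from 1/20 = 0.05 to 3/10 = 0.30. A tracer taken up by 95% of nodes at random matches 0.95.

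Two simulations of 20 specimens, with every biological input assumed, give:

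| Statistic | Selective tracer | Tracer marking nearly all nodes |
|---|---|---|
| Simulation 1: share of nodes matched | 0.13 | 0.95 |
| Simulation 1: correlation of node counts by segment | 0.33 | 0.97 |
| Simulation 1: phi, tracer-positive against involved | 0.25 | 0.00 |
| Simulation 2: correlation of node counts by specimen | 0.21–0.22 | 0.98 |
| Simulation 2: location agreement | 0.14–0.20 | 0.96 |
| Simulation 2: phi, tracer-positive against involved | 0.14–0.23 | about 0.00 |
| Simulation 2: AUC, uptake against involvement | 0.65–0.70 | about 0.50 |

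- Simulation 1 (2,000 trials) assumes 10–20 nodes, 1–3 sentinel nodes, six segments, 35% of patients node-positive with at least one sentinel node involved, and 8% of their other nodes involved.
- Simulation 2 (1,500 replicates per scenario) assumes a mean of 12 or 20 nodes, two sentinel nodes, and 30% or 50% of patients node-positive. Sentinel uptake is uniform on 0.08–0.60 of injection-site activity and other nodes on 0–0.105. The non-selective tracer puts every node on 0.08–0.60.

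Hand check of simulation 2. The share of sentinel nodes over 10% is (0.60 − 0.10)/(0.60 − 0.08) = 0.96, and of other nodes (0.105 − 0.10)/0.105 = 0.048. With 12 nodes, the selective tracer marks (2 × 0.96 + 10 × 0.048)/12 = 0.20 of them. With 20 nodes, it marks (2 × 0.96 + 18 × 0.048)/20 = 0.14. Both agree with the table.

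**Step 4: the other reading.** If pathology findings means metastatic status and the probe side means nodes positive by the 10% rule, the comparison is the phi row. The selective tracer then ranks higher. One sentence thus admits two readings that rank the tracers in opposite order.

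**The case against.** The strongest reply is that the protocol does state the right analysis. Objective D names the unit, the variables and the type of analysis, and nothing in 12.1 withdraws it. A team reading the whole document could run it. This stands: a reader might infer that uptake is never to be analysed against pathology, and that would be wrong. What remains is that the statistical section puts another statistic in its place.

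A reader might also infer that the plan as written rewards a non-selective tracer. The documents do not settle that. Section 8 includes metastatic status among what the pathologist records, and on that reading the ranking is correct. The trial has one tracer arm and ranks nothing, and the simulated tracers are extreme cases built on outside assumptions.

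A third inference would be that a misleading correlation could release the in-vivo part. The two stages are sequential in the background section, but no passage makes this result a condition for the second.

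Finally, outcome measure D is worded as accuracy for sentinel nodes; per-node uptake appears only in its objective. Tumour involvement is not a reference standard for being sentinel, since a true sentinel node can be tumour-free. Correlating uptake with involvement therefore cannot by itself deliver outcome D.

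**Conclusion.** The mismatch holds on the text alone, without any assumption: 12.1 contains no analysis of tracer uptake, continuous or by the 10% rule, against histopathology or tumour status. Outcome A and the per-node part of objective D have no matching statistic there, and 12.1 also limits its pathology comparison to the ex-vivo part although outcome A is not so limited.

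The further consequence, that a tracer marking every node would score above a selective one, is conditional on reading the sentence as probe-found against pathologist-found nodes. That reading is natural, because objective D has the pathologist identify nodes systematically, but it is not the only one. The gap of 0.96 against 0.14–0.20 shows direction under assumed inputs and predicts nothing about this trial.

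These are secondary outcomes of a feasibility study with no hypothesis test. The change should be made, but the point does not undermine the primary outcomes.

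**What to change.** In 12.1, replace the presence-and-location sentence with the following.

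- **Outcome A and objective D, ex-vivo, per node:** relate probe activity, as a percentage of injection-site activity and by the 10% rule, to metastatic status and to position. Name the measure (for example AUC for the percentage, and a two-by-two table for the rule). Allow for clustering of nodes within patients, for example by resampling whole patients.
- **Outcome D, per patient:** among ex-vivo patients with at least one involved node, report the share with at least one involved tracer-positive node, and its complement, the false-negative rate, with exact confidence intervals.
- **Outcome A, in-vivo:** report uptake against histopathology for the removed nodes, as description only.
- **Presence and location agreement:** keep it as a description of the map, and state that it is not evidence of accuracy.

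Cost: per-node activity, position and involvement in the ex-vivo part are already to be recorded. For the in-vivo part, the protocol has the probe used and the node sent for histology but does not say that the reading is kept, so the CRF should be checked. The analysis is slightly longer, and the reported correlation will probably be lower than a location agreement.

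Intervals will be wide. If 30% to 50% of the 20 ex-vivo patients are node-positive (an assumption), m = 6 to 10. With no false negatives at all, the exact 95% upper limit is 1 − 0.025^(1/m): 1 − 0.025^(1/6) = 0.46 and 1 − 0.025^(1/10) = 0.31. The report should say so.

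### Section 12.1 compares node presence and location with pathology by correlation, which does not measure agreement or accuracy; proportions and distances should replace it

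*Combined protocol and SAP*

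**What the plan says.** Section 12.1 gives one rule for setting the ex-vivo findings on nodes against pathology. It names two attributes, presence and location, and says that "lymph nodes in the mesorectal specimen will be compared with the pathology findings for each patient in the ex-vivo part using correlation". It does not state a coefficient, a unit of analysis, a coding or a coordinate system.

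Section 5 uses the same word for the accuracy outcome, secondary outcome [D]: "Accuracy of the SentiMag hand-held probe/ tracer in identifying 'sentinel' lymph nodes, determined by correlation with histopathology". The matching objective adds: "The level of tracer activity in each lymph node will be measured and correlated with position and tumour cell involvement". Secondary outcome [A] is a further correlation, of histopathology with tracer uptake.

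The reference reading is described in Section 8. A colorectal pathologist will "identify all the lymph nodes present and whether or not they contain metastatic cancer deposits". A node counts as positive on the probe when it is recorded as "having over 10% of the tracer activity of the site of initial submucosal injection" (Section 12.1).

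Section 12.2 says that the 20 ex-vivo patients are recruited to establish how accurately sentinel nodes are detected. Neither the protocol nor its statistics section names a share of confirmed peaks, a sensitivity, a false-negative rate or a distance measure between probe and pathology.

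**The concern.** Whether the probe and the pathologist point to the same nodes is a question of agreement. A correlation answers a different one: whether two variables move together across units. The two can part company. When both methods find nearly every node, presence hardly varies and the correlation has little or nothing to work on. When one method is displaced by a fixed distance, the positions still move together perfectly.

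At stake is the ex-vivo part's ability to say, in numbers, how often a probe peak is a real node and how close the two lie. As written, the analysis may give no value for a specimen with perfect agreement, a slightly negative value for one with very good agreement, and a high value for a map that is systematically displaced.

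**Working it through.** **The plan's own figures.** No coefficient, target or precision is stated for this comparison, so there is none to reproduce. The only related figures are the sample sizes: 20 ex-vivo + 20 in-vivo = 40, which agrees with the synopsis. All node counts and distances below are assumptions for illustration; the documents give none.

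**Presence: formula.** Let a = found by both, b = probe only, c = pathology only, d = neither. The correlation of two yes/no variables is

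phi = (ad - bc) / sqrt[(a+b)(c+d)(a+c)(b+d)].

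**Layout 1: nodes found by either method.** A place with no node is not a unit, so d = 0 and

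phi = -bc / sqrt[(a+b)·c·(a+c)·b].

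The numerator cannot be positive, and the denominator is zero whenever b = 0 or c = 0.

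| a, b, c (assumed) | probe findings confirmed, a/(a+b) | pathology nodes found, a/(a+c) | phi |
|---|---|---|---|
| 12, 0, 0 | 12/12 = 100% | 12/12 = 100% | undefined |
| 11, 1, 1 | 11/12 = 92% | 11/12 = 92% | -1/12 = -0.08 |
| 8, 2, 2 | 8/10 = 80% | 8/10 = 80% | -4/20 = -0.20 |
| 3, 1, 9 | 3/4 = 75% | 3/12 = 25% | -9/sqrt(432) = -0.43 |

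Enumerating a from 0 to 30 and b and c from 0 to 15 (with a+b+c > 1) gives 7,932 tables. Of these, 957 are undefined and all the others are negative; the largest value is -0.032.

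**Layout 2: the pathologist's list only.** Every unit is present on pathology, so that variable is constant and has zero variance. The correlation is undefined for every specimen.

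**Layout 3: specimen sectors.** Here a neither cell exists and phi can be positive. Take a = 14, b = c = 1 and vary only the number of empty sectors:

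- d = 1: (14 - 1)/(15 × 2) = 13/30 = 0.43
- d = 5: (70 - 1)/(15 × 6) = 69/90 = 0.77
- d = 10: (140 - 1)/(15 × 11) = 139/165 = 0.84

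The share of confirmed findings is 14/15 = 93% in all three. The coefficient depends on how finely empty tissue is divided, and the plan defines no grid.

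**Location.** For positions p, a constant shift k leaves the covariance and variances unchanged, so r(p, p + k) = 1; likewise r(p, 2p) = 1. With measurement error (15 assumed nodes over 150 mm, error SD 3 mm), Pearson's r was set beside Lin's concordance coefficient, which does penalise a shift:

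| constant offset | Pearson r | concordance coefficient |
|---|---|---|
| 0 mm | 0.998 | 0.997 |
| 10 mm | 0.998 | 0.973 |
| 20 mm | 0.998 | 0.899 |
| 40 mm | 0.998 | 0.687 |

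**What does not use this correlation.** Mapping outcome [C] is "Mapping of the distribution of tracer in the mesorectal specimen using the SentiMag hand-held probe after rectal cancer surgery", which is descriptive. The detection rate in Section 12.1 is a proportion of patients or specimens. The MRI and probe maps are compared qualitatively.

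**The case against.** The strongest reply is that the sign result needs a layout the documents do not fix. Section 12.1 defines negative as well as positive nodes, and pathology findings include metastatic status. The comparison could therefore be read as hot or cold against tumour involvement. With an assumed 15-node list (2 hot and involved, 1 hot only, 0 involved only, 12 neither), phi = 24/sqrt(3 × 12 × 2 × 13) = 0.78. This stands as a limit: undefined or negative is a property of node-list layouts, not of every layout. It does not rescue the sentence, which concerns presence and location and contains no tracer level. Tracer against tumour is the business of outcome [A], "Correlation between histopathology findings and tracer uptake (determined by Sentimag probe) in the lymph nodes", and of the objective behind [D]. That reading is also undefined in a patient with no involved nodes.

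Second, the word may be meant loosely, as a case-by-case comparison; Section 12.7 describes the measures as simple. That is possible, but the sentence then specifies no analysis at all, and the remedy is the same.

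Third, the probe detects tracer, not nodes. Nodes beyond the sentinel node may properly be cold, so 3, 1, 9 need not mean a poor probe. This stands. It means that the share of all pathology nodes with signal must not be read as a performance measure.

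A reader might go further and infer that the ex-vivo mapping result is wrong however well the probe performs. The documents do not support that. With no offset and no error, a location r of 1 is a fair description; the plan reports no offset; and the mapping outcome, the detection rate and the MRI comparison do not use this coefficient. Nor does any section make opening the in-vivo part depend on it, so an effect on that part is inference.

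**Conclusion.** The point holds in a limited form. The plan names correlation where a measure of agreement is needed, and nothing elsewhere supplies one between probe and pathology. On either node-based layout the presence coefficient is undefined or negative at any level of agreement. On a sector layout it depends on an unstated grid. For location it cannot detect a constant offset or a scale error.

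The consequence falls on the node-by-node comparison and on accuracy outcome [D], both secondary, in a 20-patient descriptive phase with no significance level. It should be corrected because Section 12.2 gives accuracy as the purpose of those 20 patients and the correction is cheap.

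The algebra does not depend on the assumed counts; the individual values do. The size of any real offset is unknown.

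**What to change.** Replace the correlation sentence in Section 12.1 with agreement measures that also serve outcome [D]. State the unit (probe peak, node) and report per specimen and overall:

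1. The share of probe peaks that the pathologist confirms as a lymph node, with an interval that allows for several nodes per patient. Treating nodes as independent, 14 of 15 would give 93.3% with an exact 95% interval of 68.1% to 99.8%; pooled across patients, such an interval would ignore the clustering.
2. As description only, the share of pathologist-identified nodes above the 10% threshold, with a note that nodes beyond the sentinel node may properly be cold.
3. Where peak and node positions are recorded on the same specimen diagram, the peak-to-node distance (median and range).

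Keep the per-node tracer level against tumour involvement for outcomes [A] and [D].

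Items 1 and 2 are a change of wording: they use the probe readings and the node list already planned. Item 3 needs positions on a shared diagram, which the protocol does not now call for; that is a small addition to data collection.
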